9.3.3 Handling of intercurrent events of primary estimand (if applicable)

The primary analysis will account for different intercurrent events as explained in the following:

- 1. Discontinuation of study treatment: Tumor assessment data collected after discontinuation of study treatment for any reason will be included to derive BOR (treatment policy strategy).
- 2. Start of a new anti-neoplastic therapy: If any new anti-neoplastic therapy is initiated, responses documented after the use of new anti-neoplastic therapy will be considered as non-response (composite strategy).
- 3. Any public health emergency as declared by local or regional authorities, i.e., pandemic, epidemic or natural disaster: Tumor assessment data collected irrespective of such unforeseen events will be considered for the BOR (treatment policy strategy).

9.3.4 Handling of missing values not related to intercurrent event

Confirmed PR or CR reported prior to any additional anticancer therapy will be considered as responses in the calculation of the ORR irrespective of the number of missed assessments before response.

Participants with a BOR of 'Not evaluable' per RECIST 1.1 will be considered as non-responders when estimating ORR. Participants who have disease progression and continue to receive study treatment after progression per RECIST 1.1 by BIRC will qualify for PD at the time of progression and will be counted as PD in the derivation of BOR.

9.3.5 Multiplicity adjustment (if applicable)

As the 2 cohorts represent different patient populations, a multiplicity adjustment for the analysis of the primary and first key secondary endpoints is not applicable. For the analysis of the other key secondary endpoints there is also no multiplicity adjustment planned.

9.3.6 Sensitivity analyses

Not applicable.

9.3.7 Supplementary analysis

A supplementary estimand is defined by the same target population, treatment of interest, intercurrent events, and summary measure as for the primary estimand. Differently from the primary estimand, the primary variable is the BOR per RECIST 1.1 assessed by the Investigator (local assessment), with responses documented after the use of any new anti-neoplastic therapy considered as non-response.

The method of analysis, handling of intercurrent events, and missing data will be the same as described in Section 9.3.2, Section 9.3.3, and Section 9.3.4.

9.4 Secondary endpoint(s)/estimand(s) analysis

The secondary objectives in this study are to assess the antitumor activity of JDQ443 singleagent as first-line treatment for participants with locally advanced or metastatic NSCLC whose tumors harbor a KRAS G12C mutation, a PD-L1 expression > 1% and an STK11 co-mutation (cohort B), and to evaluate the duration of response (DOR), disease control rate (DCR), progression-free survival (PFS), time to response (TTR), overall survival (OS), pharmacokinetics, safety, as well as patient-reported symptoms, impacts, functioning and tolerability with patient-outcomes (PRO).

ORR per RECIST 1.1 by BIRC for cohort B and DOR per RECIST 1.1 by BIRC in both cohorts are identified as the key secondary endpoints. No multiplicity adjustment is foreseen in the analysis of the key secondary or other secondary endpoints.

9.4.1 Efficacy and/or pharmacodynamic endpoint(s)

The secondary efficacy endpoints will be assessed using the FAS.

9.4.1.1 Key secondary endpoints

For the key secondary endpoint, ORR per RECIST 1.1 by BIRC in cohort B, the same definition as in Section 9.3.1 applies.

Treatment with JDQ443 will be considered to have clinically relevant efficacy in cohort B if an ORR of > 40% is observed with the lower bound of the 95% confidence interval $\ge 20\%$. The following statistical hypotheses will be tested:

 H_0 : ORR < 20% vs. H_1 : ORR > 20%.

The test will be performed based on the exact confidence interval for ORR using a one-sided α =0.025 level. The null hypothesis will be rejected if the lower bound of the two-sided 95% exact CI is \geq 20%. The ORR and its 95% confidence interval will be presented.

An interim analysis for futility will be performed to assess the ORR in approximately the first participants. Evaluable participants are defined as enrolled participants who have been followed for at least two tumor assessments or have discontinued the study earlier (see Section 9.8).

As a supportive analysis, ORR per RECIST 1.1 as assessed by local review along with 95% confidence intervals will be presented for both cohort A and cohort B.

DOR only applies to participants whose best overall response is CR or PR according to RECIST 1.1 by BIRC. The start date is the date of first documented response of CR or PR (i.e. the start date of response, not the date when response was confirmed), and the end date is defined as the date of the first documented progression or death due to any cause. Participants continuing without progression or death will be censored at the date of their last adequate tumor assessment.

DOR will be listed and summarized by cohort for all participants with confirmed BOR of CR or PR. The DOR distribution will be estimated using the Kaplan-Meier method, and the Kaplan-Meier curves, medians and 95% confidence intervals of the medians will be presented for each cohort.

As a supportive analysis, DOR per RECIST 1.1 as assessed by local review, will be summarized by cohort.

9.4.1.2 Other secondary efficacy endpoints

DCR is defined as the proportion of participants with a BOR of confirmed CR, PR and stable disease (SD) according to RECIST 1.1 (see Appendix 8 Section 10.8). DCR will be assessed by BIRC as well as by local review. DCR and the corresponding 95% confidence intervals based on the exact binomial distribution (Clopper and Pearson 1934) will be presented.

PFS is defined as the time from the date of first dose of study treatment to the date of the first documented progression or death due to any cause. PFS will be assessed by BIRC as well as by local review according to RECIST 1.1 (see Section 10.8 for further details). PFS will be censored if no PFS event is observed before the first to occur between: (i) the analysis cut-off date, and (ii) the date when a new anti-neoplastic therapy is started. The censoring date will be the date of the last adequate tumor assessment prior to cut-off/start of new anti-neoplastic therapy. The PFS distribution will be estimated using the Kaplan-Meier method, and the Kaplan-Meier curves, medians and 95% confidence intervals of the medians will be presented for each cohort.

Time to response (TTR) is defined as the time from the date of first dose of study treatment to the first documented response of either CR or PR, which must be subsequently confirmed (although date of initial response is used, not date of confirmation). CR and PR are based on tumor response data by BIRC as well as per local review and according to RECIST 1.1 (see Section 10.8 for details). All participants in the FAS will be included in TTR calculations. Participants without a confirmed CR or PR will be censored at the study-maximum follow-up time (i.e., LPLV-FPFV) for participants with a PFS event (i.e., disease progression or death due to any cause), or at the date of the last adequate tumor assessment for participants without a PFS event. TTR will be listed and summarized by cohort. The TTR distribution will be estimated using the Kaplan-Meier method, and the Kaplan-Meier curves, medians and 95% confidence intervals of the medians will be presented for each cohort.

OS is defined as the time from the date of first dose of study treatment to the date of death due to any cause. If a participant is not known to have died, then OS will be censored at the latest date the participant was known to be alive (on or before the cut-off date). The OS distribution will be estimated using the Kaplan-Meier method, and the Kaplan-Meier curves, medians and 95% confidence intervals of the medians will be presented for each cohort.

9.4.2 Safety endpoints

For all safety analyses, the safety set will be used. All listings and tables will be presented by cohort.

Safety summaries (tables, figures) include only data from the on-treatment period with the exception of baseline data which will also be summarized where appropriate (e.g., change from

baseline summaries). In addition, a separate summary for death including on treatment and post treatment deaths will be provided. In particular, summary tables for adverse events (AEs) will summarize only on-treatment events, with a start date during the on-treatment period (treatment-emergent AEs).

The overall observation period will be divided into three mutually exclusive segments:

- 1. Pre-treatment period: from day of participant's informed consent to the day before first dose of the study treatment
- 2. On-treatment period: from day of first dose of the study treatment to 30 days after last dose of the study treatment
- 3. Post-treatment period: starting at day 31 after last dose of the study treatment.

9.4.2.1 Adverse events

All information obtained on AEs will be displayed by cohort and participant.

The number (and percentage) of participants with treatment emergent AEs (events started after the first dose of study medication or events present prior to start of treatment but increased in severity based on preferred term) will be summarized in the following ways:

- By treatment, primary system organ class and preferred term
- By treatment, primary system organ class, preferred term and maximum severity

Separate summaries will be provided for study medication related AEs, deaths, SAEs, other significant AEs leading to discontinuation, and AEs leading to dose adjustment.

The number (and proportion) of participants with adverse events of special interest (AESI) will be summarized by cohort. AESIs will be defined based on the case retrieval strategy (CRS) available at the time of the analysis.

A participant with multiple AEs within a primary system organ class is only counted once towards the total of the primary system organ class.

All deaths (on-treatment and post-treatment) will be summarized.

All AEs, deaths and serious adverse events (including those from the pre- and post-treatment periods) will be listed and those collected during the pre-treatment and post-treatment period will be flagged.

9.4.2.2 Clinical laboratory evaluations

Grading of laboratory values will be assigned programmatically as per CTCAE version 5.0. The calculation of CTCAE grades will be based on the observed laboratory values only, clinical assessments will not be taken into account.

CTCAE Grade 0 will be assigned for all non-missing values not graded as 1 or higher. Grade 5 will not be used. For laboratory tests where grades are not defined by CTCAE version 5.0, results will be categorized as low/normal/high based on laboratory normal ranges.

All laboratory data will be summarized by cohort. The following summaries/listings will be generated separately for hematology and biochemistry tests:

• Listing of all laboratory data with values flagged to show the corresponding CTCAE version 5.0 grades if applicable and the classifications relative to the laboratory normal ranges

For laboratory tests where grades are defined by CTCAE version 5.0

- Worst post-baseline CTCAE grade (regardless of the baseline status). Each participant will be counted only once for the worst grade observed post-baseline
- Shift tables using CTCAE version 5.0 grades to compare baseline to the worst ontreatment value

For laboratory tests where grades are not defined by CTCAE version 5.0,

• Shift tables using the low/normal/high/ (low and high) classification to compare baseline to the worst on-treatment value.

In addition to the above-mentioned tables and listings, other exploratory analyses, for example figures plotting time course of raw or change in laboratory tests over time or box plots may be specified in the analysis plan.

9.4.2.3 Vital signs

Vital signs parameter measured include blood pressure (supine position preferred when ECG is collected), pulse measurement, respiratory rate and body temperature.

Data on vital signs will be tabulated and listed by cohort, visit/time, notable values will be flagged. Summary statistics will be provided by cohort.

9.4.2.4 12-lead ECG

PR, QRS, QT, QTcF, and RR intervals will be obtained from 12-lead ECGs for each participant during the study. ECG data will be read and interpreted centrally.

Notable ECG abnormalities will be summarized. In addition, a listing of these participants will be produced by cohort.

9.4.3 Pharmacokinetics

The FAS will be used to list individual concentration data. The PAS will be used for summary statistics of JDQ443 concentration data and the FPAS for all PK analyses (non-compartmental and pharmacometric) including summary statistics of PK parameters.

JDQ443 concentration data will be listed by cohort, participant, and visit/sampling time point. Descriptive summary statistics will be provided by cohort and visit/sampling time point, including the frequency (n, %) of concentrations below the LLOQ and reported as zero.

Summary statistics of concentration data will include mean (arithmetic and geometric), SD, CV (arithmetic and geometric), median, minimum, and maximum. Concentrations below LLOQ will be treated as zero in summary statistics and for PK parameter calculations. A graphical presentation will be provided on mean concentration at each scheduled time point when the full PK profile is available.

Individual and mean PK parameters such as listed in Table 9-1 will be derived using non-compartmental analysis using Phoenix WinNonlin (Version 5.0 or higher) and reported, if feasible.

Descriptive summary statistics of PK parameters will include mean (arithmetic and geometric), SD, and CV (arithmetic and geometric), median, minimum, and maximum. An exception to this is T_{max} where median, minimum, and maximum will be presented.

Table 9-1 JDQ443 plasma pharmacokinetic parameters - non-compartmental analysis

The AUC from time zero to the last measurable concentration sampling time (t _{lastss}) at steady-state (mass × time × volume ⁻¹)
The AUC calculated to the end of a dosing interval (tau) at steady-state (amount × time × volume ⁻¹)
The maximum (peak) observed plasma, blood, serum, or other body fluid drug concentrations after single dose administration (mass × volume ⁻¹)
The time to reach maximum (peak) plasma, blood, serum, or other body fluid drug concentration at stead-state (time)
Observed concentration at the end of a dosing interval (taken directly before next administration) at steady-state
Smallest (slowest) disposition (hybrid) rate constant (time ⁻¹) may also be used for terminal elimination rate constant at steady-state (time ⁻¹)
The elimination half-life associated with the terminal slope (λ_z) of a semi logarithmic concentration-time curve at steady-state (time).
The total body clearance of drug from the plasma (volume × time ⁻¹)
The apparent volume of distribution during terminal phase (associated with λ_{z}) (volume)

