8.8.1 Pharmacokinetic blood collection and handling

PK blood samples will be taken by either direct venipuncture or an indwelling cannula inserted in a forearm vein at the visits defined in the pharmacokinetic log (Table 8-7 or Table 8-8). Refer to the laboratory manual for detailed instructions regarding sample collection, numbering, processing and shipment.

Complete dosing and blood sampling information, including the date/time of actual blood draw and date/time of the last study treatment dose prior to the sampling, should be obtained on all sampling days and recorded on the PK eCRF. Time of vomiting, if it occurs within 4 hours following investigational drug(s) administration, should be documented in eCRF. Meal date/time before and after JDQ443 administration should be collected on the PK collection days.

An unscheduled PK blood sample will be collected, 1) if a participant experiences an AE suspected to be related to study treatment that results in an unscheduled visit or fits the criteria of an SAE, 2) whenever an unscheduled post-baseline tumor sample is collected during the treatment.

The date and time of the unscheduled blood sample collection, and the date, time and dose of the investigational drug taken prior to the unscheduled blood sample collection should be entered in the appropriate eCRF.

On days and time points where blood PD samples are to be drawn, the PK sample should be drawn first. On days and time points where ECG are collected, take ECG prior to PK blood draw.

For approximately 10 participants in each of the Cohorts (A and B), PK blood samples will be collected at time-points described in Table 8-7 (Intensive PK sampling scheme). Approximately 2 participants from this intensive PK group will be from China. For the remaining participants in each of the Cohorts (A and B), standard PK blood samples will be collected at time-points described in Table 8-8 (standard PK sampling scheme).

Table 8-7 PK blood collection log for JDQ443 treatment (intensive sampling; for approximately 10 participants in Cohort A and approximately 10 participants in Cohort B)

Treatment Period or Cycle	Day	Scheduled Time Point	Dose reference ID	Sample number	Analyte
1	1	hour* /pre-dose	11	101	JDQ443
1	1	hour (± 30 minutes)	11	102	JDQ443
1	1	hour (± 30 minutes)	11	103	JDQ443
1	15	hour* /pre-dose	12 / 121#	104	JDQ443
1	15	hour (±10 minutes)	12	105	JDQ443
1	15	hours (±15 minutes)	12	106	JDQ443
1	15	hours (±15 minutes)	12	107	JDQ443

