9.1 Analysis sets

The Full Analysis Set (FAS) comprises all participants to whom study treatment has been assigned and who received at least one dose of study treatment.

The Safety Set includes all participants who received at least one dose of study treatment.

The FAS and Safety Set in this study are identical.

The Pharmacokinetic Analysis Set (PAS) includes all participants who received at least one planned dose of study treatment and provide an evaluable pharmacokinetic concentration.

Criteria described below need to be considered for a concentration to be evaluable:

- Participant did not vomit within 4 hours after dosing of JDQ443
- For all pre-dose samples, PK draw occurred before the next dose intake
- For post-dose PK samples, PK draw with concentration following planned dose
- Any PK blood samples with missing collection date or time, or missing associated study treatment dosing date or time will be excluded.

The Full Pharmacokinetic Analysis Set (FPAS) includes PAS participants with intensive PK collection schedule who provide an evaluable PK profile. A profile is considered evaluable if the conditions listed for the PK Analysis Set (Section 9.4.3) and the following conditions are met:

- Participant receives planned dose
- Participant provides at least one valid primary PK parameter

Further details will be included in the Statistical Analysis Plan (SAP).

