9.5.1.2 Data analysis principles

The FAS will be used for all biomarker analyses unless otherwise specified.

Depending on the endpoint of interest, graphical displays such as box plots or strip plots may be used to assess the relationship of different biomarkers with clinical benefit. These may be separated by cohort and include either baseline or change from baseline values, where applicable.

For continuous markers, baseline and change from baseline (absolute change, percent change and fold change) at each time point will be summarized in tables that include sample size, mean, standard deviation, CV%, median, minimum and maximum. For fold change from baseline, geometric mean and geometric CV% will also be included. For categorical markers such as mutation status, 2×2 contingency tables may be used to assess the relationship with clinical benefit and/or Kaplan-Meier curves may be generated given the number of events warrant such an assessment.

If additional analyses are needed to be performed after the completion of the end-of-study clinical study report (CSR), they will be documented in separate reports. The data analysis will be described in an addendum of the statistical analysis plan (SAP) or in a stand-alone analysis plan document, as appropriate.

9.5.2 **Pharmacokinetics**

Pharmacokinetic data from this study will be analyzed using population PK approach, which may include exploring the effect of covariates on PK, if data allow. The PK data from this study may be combined with similar data from other studies and explored using population PK. Exploratory analyses may also be conducted to identify possible relationships of JDQ443 exposure (e.g., Cmax, Cmin or AUC) with PD markers, clinical efficacy (ORR, PFS, and OS) or safety variables as appropriate. The results of such exploratory analyses will be reported separately from the CSR.

9.6 (Other) Safety analyses

Not applicable

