2.2 Analysis sets

Participants are considered to be enrolled into the study if they have signed the main informed consent. Only participants who have signed the main informed consent will be included in the analysis data sets.

Participants who signed a molecular pre-screening informed consent form but failed to meet pre-screening criteria, as well as participants who signed the main informed consent form and were subsequently found to be ineligible (have failed to meet inclusion or exclusion criteria) will be considered screen failures.

Full Analysis Set

The Full Analysis Set (FAS) comprises all participants to whom study treatment has been assigned and who received at least one dose of study treatment. Participants will be analyzed according to the cohort they have been assigned to. Participants may be enrolled based on PD-L1 expression status and the presence of a KRAS G12C mutation and STK11 mutation (cohort B only) determined by a validated local test or a central test in tumor tissue or blood.

Safety Set

The Safety Set includes all participants who received at least one dose of study treatment.

The FAS and Safety Set in this study are identical.

Pharmacokinetic Analysis Set

The Pharmacokinetic Analysis Set (PAS) includes all participants who received at least one planned dose of study treatment and provide an evaluable pharmacokinetic concentration.

The criteria below need to be considered for a concentration to be evaluable:

- Participant did not vomit within 4 hours after dosing of JDQ443
- For all pre-dose samples, PK draw occurred before the next dose intake
- For post-dose PK samples, PK draw with concentration following planned dose
- Any PK blood samples with missing collection date or time, or missing associated study treatment dosing date or time will be excluded

Full Pharmacokinetic Analysis Set

The Full Pharmacokinetic Analysis Set (FPAS) includes PAS participants with extensive PK collection schedule who provide an evaluable PK profile. A profile is considered evaluable if the conditions listed for the PAS and the following conditions are met:

- Participant received the planned dose
- Participant provides at least one valid primary PK parameter

PK blood samples with missing collection date or time or missing associated JDQ443 dosing date or time will be excluded.

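### Protocol 9.4.3 ties pharmacometric analyses to the intensively sampled PK set (about 20 of 120 participants), in conflict with 9.5.2 and with PK sampling of all participants (minor)

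*Protocol*

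**What the plan says.** **Which set serves which analysis.** Protocol 9.4.3 lists individual concentrations on the FAS, summarizes concentrations on the PAS, and uses "the FPAS for all PK analyses (non-compartmental and pharmacometric) including summary statistics of PK parameters".

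**Who is in each set.** In Protocol 9.1 the PAS "includes all participants who received at least one planned dose of study treatment and provide an evaluable pharmacokinetic concentration". The FPAS "includes PAS participants with intensive PK collection schedule who provide an evaluable PK profile", and the participant must also supply at least one valid primary PK parameter. SAP 2.2 keeps the same restriction with one word changed: the FPAS "includes PAS participants with extensive PK collection schedule who provide an evaluable PK profile".

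**Who is sampled how.** Protocol 8.8 takes serial samples from every participant in order to characterize the PK. Protocol 8.8.1 then splits the schedules. "For approximately 10 participants in each of the Cohorts (A and B), PK blood samples will be collected" on the intensive scheme of Table 8-7. "For the remaining participants in each of the Cohorts (A and B), standard PK blood samples will be collected" on the scheme of Table 8-8.

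**What modeling is planned.** Protocol 9.5.2 states: "Pharmacokinetic data from this study will be analyzed using population PK approach". Covariates may be explored, the data may be combined with other studies, and exposure may be related to ORR, PFS, OS and safety. No analysis set is named.

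**The SAP.** SAP 2.10 says that both the PAS and the FPAS will be used. It lists concentrations on the PAS, but otherwise does not say which set serves which analysis. It describes concentration summaries and non-compartmental parameters only.

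**The concern.** Requiring an intensive profile makes sense for non-compartmental analysis, where each participant's own curve must support an AUC or a half-life. It does not make sense for a mixed-effects population model, whose main advantage is that it can use a few samples from each of many participants. Yet 9.4.3 puts both kinds of analysis on the same restricted set. The rest of 9.4.3 covers only concentration summaries and non-compartmental parameters, so its reference to pharmacometric work most naturally points to the population PK of 9.5.2.

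An analyst who follows 9.4.3 would fit the population model, and any exposure-response model, to a small fraction of the trial. An analyst who uses all the data would depart from the set that the protocol states. Either way, the choice of dataset is left to be argued later instead of being fixed in advance.

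**Working it through.** This is a counting exercise; no power formula applies.

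**Inputs**
- Planned enrollment: 90 in cohort A and 30 in cohort B (Protocol 9.9).
- Intensive schedule: about 10 participants per cohort (Protocol 8.8.1; title of Table 8-7).
- Scheduled samples per participant, intensive: numbers 101 to 114 in Table 8-7, so 14.
- Scheduled samples per participant, standard: numbers 101–104, 108, 109 and 112–114 in Table 8-8, so 4 + 2 + 3 = 9. Biopsy-linked and unscheduled samples are not counted.
- Sample 101 is the C1D1 pre-dose sample in both tables.

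**Step 1. The plan's own total.** 90 + 30 = 120, which matches the stated 120.

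**Step 2. Largest possible FPAS.** 10 + 10 = 20, and 20/120 = 16.7%.

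**Step 3. Participants outside it.** 120 − 20 = 100, or 83.3%. By cohort this is 90 − 10 = 80 of 90 in A and 30 − 10 = 20 of 30 in B. Half of the FPAS would come from cohort B, which is 30/120 = 25% of the trial.

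**Step 4. Scheduled samples at full attendance.**
- Intensive: 20 × 14 = 280.
- Standard: 100 × 9 = 900.
- Share left out of modeling: 900/(280 + 900) = 900/1,180 = 76%.
- After the first dose only: standard 100 × 8 = 800, intensive 20 × 13 = 260, share 800/1,060 = 75%.

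**Step 5. If a cohort stops for futility**, taking the planned interim sizes of about 30 and 15 and assuming that 10 intensive participants per cohort are already enrolled:
- A stops: 30 + 30 − 20 = 40 of 60 outside the FPAS.
- B stops: 90 + 15 − 20 = 85 of 105.
- Both stop: 30 + 15 − 20 = 25 of 45.

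The absolute loss shrinks, but more than half of the participants remain outside the set in every case.

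**Step 6. A wording check.** Footnote 19 of Table 1-3 could be read as about 10 intensive participants in total, which would leave 110 outside. Section 8.8.1 and the title of Table 8-7 both say 10 per cohort, so 20 is used here.

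**Step 7. Does any visible text lift the restriction?** Protocol 9.5.2 speaks of the study's PK data in general but names no set. SAP 2.10 mentions both sets but describes no population PK. Neither overrides the explicit assignment in 9.4.3.

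**The case against.** The strongest reply is that this is one stray word in a section about secondary endpoints. Population PK has its own section, whose subject is the PK data of the study and not the FPAS. Every participant is sampled, and the sponsor would hardly collect standard-schedule samples only to leave them out of the model. SAP 2.10 does not repeat the restriction and admits the PAS to PK data analysis. Part of the exploratory text is also unavailable: the visible SAP numbering goes from 2.11.3, which ends in a redaction, to 2.15, and the exploratory rows of Protocol Table 3-1 are missing. A set for modeling may be named there.

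Most of this stands. A drafting error is the likely explanation, and the finding is limited to the visible text. It does not remove the conflict, because 9.4.3 is an explicit assignment and nothing visible corrects it.

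The objection does rule out some stronger readings that a reader might infer:
- **That the sparse data are discarded.** The documents do not support this. The protocol lists these concentrations on the FAS and summarizes them on the PAS.
- **That the main results or the secondary PK results are compromised.** They are not. The FPAS is a suitable set for non-compartmental analysis. Under 9.5.2, population PK and exposure-response are exploratory and reported separately from the CSR.
- **That a definite number of responders would be lost to exposure-response.** That work is optional, and any such number needs an assumed ORR and assumes that both cohorts continue.

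**Conclusion.** The conflict is real, and it is minor. Taken literally, 9.4.3 bases population PK and any exposure-response analysis on at most about 20 of 120 participants and omits about 900 scheduled standard-schedule samples, about 800 of which follow the first dose. These figures assume full enrollment with neither cohort stopped, 10 intensive participants per cohort, and full attendance. Participants who stop before C5D1 or C7D1 would lower the sample count.

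The consequence is confined to exploratory modeling outside the CSR. No primary, key secondary or non-compartmental result depends on it. Whether redacted text already names a modeling set cannot be determined from the public documents.

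**What to change.** Three wording changes:
1. In Protocol 9.4.3, assign the FPAS to non-compartmental analysis and the summary statistics of PK parameters, and drop the reference to pharmacometric work.
2. In Protocol 9.5.2, name the PAS (all evaluable concentrations from both the intensive and the standard schedules) as the set for population PK and exposure-response.
3. State the same mapping in SAP 2.10, or in the modeling plan if there is a separate one.

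No new samples, visits or assessments are needed, because the standard schedule is already in the protocol. Protocol 10.1.8.1 requires a written amendment for any protocol change, so the two protocol edits can wait for the next amendment. The statement in the SAP or modeling plan can be made sooner and should be in place before modeling starts.
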